5.5.2 Sponsor Follow-Up

For SAEs, AESIs, and pregnancies, the Sponsor or a designee may follow up by telephone, fax, e-mail, and/or a monitoring visit to obtain additional case details and outcome information (e.g., from hospital discharge summaries, consultant reports, autopsy reports) in order to perform an independent medical assessment of the reported case.

5.6 ADVERSE EVENTS THAT OCCUR AFTER THE ADVERSE EVENT REPORTING PERIOD

The Sponsor should be notified if the investigator becomes aware of any SAE that occurs after the end of the AE reporting period (defined as 5 months after the final dose of study drug), if the event is believed to be related to prior study drug treatment. These events should be reported through use of the Adverse Event eCRF. However, if the EDC system is not available, the investigator should report these events directly to the Sponsor or its designee, either by faxing or by scanning and emailing the paper Clinical Trial Serious Adverse Event/Adverse Event of Special Interest Reporting Form using the fax number or e-mail address provided to investigators.

5.7 EXPEDITED REPORTING TO HEALTH AUTHORITIES, INVESTIGATORS, INSTITUTIONAL REVIEW BOARDS, AND ETHICS COMMITTEES

The Sponsor will promptly evaluate all SAEs and AESIs against cumulative product experience to identify and expeditiously communicate possible new safety findings to investigators, IRBs, ECs, and applicable HAs based on applicable legislation.

To determine reporting requirements for single AE cases, the Sponsor will assess the expectedness of these events using the following reference document:

- RO7234292 Investigator's Brochure

The Sponsor will compare the severity of each event and the cumulative event frequency reported for the study with the severity and frequency reported in the applicable reference document.

Reporting requirements will also be based on the investigator's assessment of causality and seriousness, with allowance for upgrading by the Sponsor as needed.

6. STATISTICAL CONSIDERATIONS AND ANALYSIS PLAN

6.1 ANALYSIS POPULATIONS

The intent-to-treat (ITT) population will consist of all patients who received any study treatment. Randomized patients who received incorrect therapy from that intended will be summarized in the group according to their planned randomized treatment.

The ITT population will be the primary population for all analyses of efficacy and biomarker variables.

The safety population will consist of all patients who received any study treatment. The safety population will be the primary population for all safety analyses. For the purpose of all safety analyses, it will be assessed whether patients received a treatment different from the one they were randomized to at any time during the course of the study. In case the number and duration of such "treatment switches" warrants it, the safety population may be redefined by reallocating individual patients to the treatment actually received, as opposed to which treatment they were randomized to.

6.2 DETERMINATION OF SAMPLE SIZE

The sample size for this study is determined by the number of patients from preceding studies who may be eligible for enrollment in this study and is estimated to be up to approximately 1100 patients.

6.3 SUMMARIES OF CONDUCT OF STUDY

The number of patients who enroll in the study, discontinue from the study, and complete the study will be summarized overall and by treatment arm. Reasons for premature study withdrawal will be listed and summarized.

6.4 SUMMARIES OF TREATMENT GROUP COMPARABILITY

Demographic and baseline characteristics will be summarized using means, standard deviations, medians, and ranges for continuous variables and proportions for categorical variables, as appropriate. Summaries will be presented overall and by treatment group.

6.5 SAFETY ANALYSES

The safety analysis population will consist of all randomized patients who received at least one dose of study drug, with patients grouped according to treatment received.

All verbatim AE terms will be mapped to Medical Dictionary for Regulatory Activities (MedDRA) thesaurus terms. The Adverse Event Severity Grading Scale (see Section 5.3.3) will be used for assessing AE severity. Laboratory values determined as an AE should be graded as per [Appendix 10](#), which is based on the NCI CTCAE (v5.0).

All safety data, including AEs, laboratory tests, neurologic examination, C-SSRS, MoCA, ECG, and vital signs, will be reported in individual listings and summarized by treatment for each assessment time using descriptive statistics. For continuous variables, both the original value as well as the change from baseline will be reported.

The incidence of AEs will be summarized on the basis of body systems and dictionary preferred terms. The incidence of AEs by severity and relationship to study drug or study procedure and incidence of marked abnormal laboratory test results will be provided.

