the preceding study) or will be the first dose in Study BN40955 if a separate inclusion visit is required (see [Appendix 1a](#)).

- After implementation of Study BN40955 Protocol Version 3, patients who are already enrolled in Study BN40955 will sign the amended Informed Consent Form (ICF) at or before their next clinic visit, and will be assigned to either the 120 mg RO7234292 Q8W or 120 mg RO7234292 Q16W arm, and then follow the schedule of activities for Protocol Version 3 (see [Appendix 1a](#))—matching treatment week according to [Appendix 2](#)—at the clinic visit and going forward.
- Patients who did not previously receive treatment with RO7234292 (e.g., from a natural history study, eligible patients from Study BN40423 study who were not randomized due to logistical challenges resulting from the COVID-19 pandemic) or received short-term treatment (≤ 4 doses) with a treatment-free follow-up period will be randomly allocated to receive 120 mg of RO7234292 Q8W or 120 mg of RO7234292 Q16W. The first dose in Study BN40955 will take place at the inclusion visit.
- Patients who previously received blinded placebo Q8W will be randomly allocated to receive 120 mg of RO7234292 Q8W or 120 mg of RO7234292 Q16W. The first dose in Study BN40955 will take place at the inclusion visit.
- Patients who previously received blinded 120 mg of RO7234292 Q8W will receive open-label 120 mg of RO7234292 Q8W.
- Patients who previously received blinded 120 mg of RO7234292 Q16W will receive open-label 120 mg of RO7234292 Q16W.

For patients who enrolled from Study ML41885, the inclusion visit will take place at the first safety follow-up visit of Study ML41885 (i.e., safety follow-up [SFU1]). The drug administered at the inclusion visit will be the first dose in Study BN40955. Patients who consent to be enrolled into this study (Study BN40955) will be assigned to a treatment group as shown below:

- Patients who received open-label 120 mg of RO7234292 Q16W will receive open-label 120 mg of RO7234292 Q16W.

Patients enrolled in Study BN40423 prior to implementation of Protocol Version 4 will be prematurely discontinued from that study. Patients who consent to be enrolled into this study (Study BN40955) will be assigned to treatment groups as shown below:

- Patients who received blinded 120 mg of RO7234292 Q4W will be randomly allocated to receive open-label 120 mg of RO7234292 Q8W or 120 mg of RO7234292 Q16W.

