- Patients who received blinded 120 mg of RO7234292 Q8W will receive open-label 120 mg of RO7234292 Q8W.
- Patients who received blinded placebo Q4W will be randomly allocated to receive open-label 120 mg of RO7234292 Q8W or 120 mg of RO7234292 Q16W.

Table 1 Treatment Regimen in Study BN40955 Based on Previous Study Treatment

Preceding Study Treatment	Treatment Regimen
Open-label 120 mg RO7234292 Q4W	Randomized 1:1 to 120 mg RO7234292 Q8W or 120 mg RO7234292 Q16W
Open-label 120 mg RO7234292 Q8W	120 mg RO7234292 Q8W
No treatment or ≤ 4 doses of 120 mg or less RO7234292 with a treatment-free follow-up period	Randomized 1:1 to 120 mg RO7234292 Q8W or 120 mg RO7234292 Q16W
Blinded placebo Q8W	Randomized 1:1 to 120 mg RO7234292 Q8W or 120 mg RO7234292 Q16W
Blinded 120 mg RO7234292 Q8W	120 mg RO7234292 Q8W
Blinded 120 mg RO7234292 Q16W	120 mg RO7234292 Q16W

Table 1 Treatment Regimen in Study BN40955 Based on Previous Study Treatment (cont.)

Preceding Study Treatment	Treatment Regimen
For Patients enrolled into Study BN40423 prior to implementation of Study BN40423 Protocol Version 4:	
Blinded 120 mg RO7234292 Q4W	Randomized 1:1 to 120 mg RO7234292 Q8W or 120 mg RO7234292 Q16W
Blinded 120 mg RO7234292 Q8W	120 mg RO7234292 Q8W
Blinded Placebo Q4W	Randomized 1:1 to 120 mg RO7234292 Q8W or 120 mg RO7234292 Q16W
Open-label 120 mg RO7234292 Q16W	120 mg RO7234292 Q16W

Q4W=every 4 weeks; Q8W=every 8 weeks; Q16W=every 16 weeks.

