4.2 METHOD OF TREATMENT ASSIGNMENT AND BLINDING

All patients in this study will have the opportunity to receive treatment with either 120 mg RO7234292 Q8W or 120 mg RO7234292 Q16W and will be assigned to treatment as described in [Table 1](#). An independent interactive voice or web-based response system (IxRS) provider will assign patients to treatment and conduct randomization where required. If, during the course of the study, a single regimen is selected for the development program, all patients will then be assigned to the selected regimen.

All patients, study site personnel, Sponsor agents, and Sponsor personnel will be unblinded to the treatment assignment of this study; however, the treatment assignment from a blinded preceding study will remain blinded until the preceding study is unblinded.

An IxRS provider will hold the treatment assignment code to maintain the integrity of the blinding (active versus placebo) in the preceding study.

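### Section 6.5 and the synopsis restrict the safety population to randomized patients, while Section 6.1 takes all treated patients and five of the ten assignment routes in Table 1 involve no randomization

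*Combined protocol and SAP*

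**What the plan says.** **Population.** Section 6.5, and the synopsis under Primary Analysis in the same words, read: "The safety analysis population will consist of all randomized patients who received at least one dose of study drug". Both group patients by the treatment they received. Section 6.1 reads: "The safety population will consist of all patients who received any study treatment". It adds: "The safety population will be the primary population for all safety analyses".

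**Grouping.** Section 6.1 first checks whether patients received something other than their randomized treatment. If the number and duration of such switches justify it, "the safety population may be redefined by reallocating individual patients to the treatment actually received", "as opposed to which treatment they were randomized to".

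**Assignment.** Table 1 in Section 3.1.1 is titled "Treatment Regimen in Study BN40955 Based on Previous Study Treatment". Some of its routes are randomized 1:1 and others fix the regimen; for example, "Patients who previously received blinded 120 mg of RO7234292 Q8W will receive open-label 120 mg of RO7234292 Q8W". Section 4.2 keeps the two acts apart: the interactive response system "provider will assign patients to treatment and conduct randomization where required".

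**The concern.** Long-term safety and tolerability are the main objective of this extension (Section 2.1). Its safety tables are descriptive, so they rest on who is in the denominator and which column each patient is in. Following Section 6.5 literally gives a different denominator from following Section 6.1.

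The difference is not neutral. Every directly assigned route consists of patients staying on the active regimen they already had. The randomized routes bring in patients from placebo, patients with no or short prior treatment, and patients coming off Q4W. A literal reading would therefore remove the patients with continuous exposure to one regimen, who are central to a long-term safety study.

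The grouping rule in Section 6.1 has a related gap. It compares treatment received with a randomized treatment, and directly assigned patients have none.

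**Working it through.** **1. Count of routes (Section 3.1.1, Table 1).**

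- Randomized 1:1 (five rows): open-label Q4W; no treatment or at most 4 doses; blinded placebo Q8W; and, from BN40423 before its Version 4, blinded Q4W and blinded placebo Q4W.
- Directly assigned (five rows): open-label Q8W, blinded Q8W and pre-Version 4 blinded Q8W, all to Q8W; blinded Q16W and open-label Q16W, both to Q16W.

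Total: 5 + 5 = 10. The open-label Q16W row sits under the pre-Version 4 subheading, although the text ties it to Study ML41885; the count is the same either way. These are rows, not patients.

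**2. The definitions applied to the routes.** Under Section 6.1, treated patients from 10 of 10 routes are in the safety population. Under Section 6.5 and the synopsis read literally, only those from 5 of 10 are.

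**3. Were directly assigned patients enrolled?** No count by route is given. Section 5.1.1 does give BN40955 event counts with percentages at 07 August 2020, from which the denominators follow.

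- Q8W: 30 patients, 22.9%. N must lie between 30/0.2295 = 130.7 and 30/0.2285 = 131.3, so N = 131.
- Q16W: 11 patients, 15.1%. N must lie between 11/0.1515 = 72.6 and 11/0.1505 = 73.1, so N = 73.
- Cross-checks: the procedural pain figures of 9.2% and 4.1% fit 12/131 and 3/73. Section 5.1.1.1 gives 7 patients (5.3%), which fits N = 131 to 133, and 2 patients (2.7%), which fits N = 73 to 75.

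Total: 131 + 73 = 204. If every patient had been randomized 1:1 independently, the expected Q8W count would be 204 × 0.5 = 102, with standard deviation √(204 × 0.5 × 0.5) = 7.14. The observed 131 is 29 above that, or 4.1 standard deviations. The exact binomial tail is P(X ≥ 131 | n = 204, p = 0.5) = 0.0000296, about 0.00003. Randomization alone is a poor explanation of this split; direct assignment to Q8W is the obvious alternative.

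**4. Grouping rules side by side.** Section 6.5 uses treatment received without condition. Section 6.1 moves patients to treatment received only if switches are judged numerous or long enough, with no criterion. The two give the same tables if nobody switches. Neither covers a patient whose doses do not reveal a regimen: a single 120 mg dose before the pause is the same under Q8W and Q16W.

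**The case against.** The best defence is that *randomized* is template wording and that the plan already points to the right population. Section 6.1 is the section on analysis populations and calls its safety population primary for all safety analyses, which comes close to a rule of precedence. The PK and immunogenicity populations (Sections 6.7 and 6.8) are not limited to randomized patients. Appendix 2b describes the whole Q8W and Q16W groups as randomized. The 131 and 73 in Section 5.1.1 suggest that the sponsor's own reporting already counts directly assigned patients. Most of this stands: the broader population is the likelier intention. It does not remove the conflict, because Section 4.2 and Table 1 use the word strictly and the narrower definition stands in both the synopsis and the section that governs the safety analyses.

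It is also fair that the grouping difference should seldom matter. Section 5.1.3.1 allows no change of dosing frequency, so switches should be uncommon.

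Three stronger readings are tempting, and the documents do not support them:

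- **That half the patients would be lost.** Five of ten counts table rows of unknown size, and blinded Q8W appears twice, once for each BN40423 protocol era.
- **That 131 − 73 = 58 of 204 patients (28%) were not randomized.** This needs an exact 1:1 split of the rest and no direct assignment to Q16W. Section 3.1.1 also lets patients already on open-label Q8W within BN40955 keep it, and does not say whether they had been randomized under an earlier protocol version. For the same reason, the sizes of the preceding studies' cohorts do not bound the number.
- **That patients given Q4W within BN40955 have no group.** Section 3.1.1 randomizes them to Q8W or Q16W. Only the attribution of their earlier Q4W time is open, and that is a detail to specify rather than part of this error.

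**Conclusion.** The inconsistency is real, and the definition in Section 6.5 and the synopsis is wrong as written for this design. Taken literally, it excludes treated patients from five of ten assignment routes, all of them continuing the same active regimen, although Section 6.1 includes them. The wider population is probably what is meant.

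The number affected cannot be derived from the documents. The 131 to 73 split makes it very likely that such patients were enrolled by August 2020. That inference assumes that the two denominators, recovered from rounded percentages, are the full treated cohorts, and that randomization was 1:1 as Table 1 states. It does not show how many patients came by each route.

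The consequence is limited to the denominators, event rates and column membership of descriptive tables. No hypothesis test or power statement is affected, and all safety data are also to be listed individually.

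**What to change.** 1. Delete *randomized* from the population sentence in Section 6.5 and in the synopsis, so that both match Section 6.1. Keep the Section 6.1 wording and do not add a condition that the dose be given in BN40955. For some entrants, such as those from BN40697 without a delayed visit, the inclusion-visit dose counts as the preceding study's last (Section 3.1.1; Appendix 1a, footnote s). Such a condition could exclude patients dosed only then.
2. In the grouping sentences of Sections 6.1 and 6.5, refer to assigned regimen, whether randomized or direct, in place of randomized treatment. Group by regimen received, without the conditional reallocation. Use assigned regimen as the fallback where the doses given do not identify a regimen, such as a single dose before the pause.
3. While editing, say how Q4W time within BN40955 is tabulated.

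The cost is one word in two places and a sentence or two on grouping. No new data or visits are needed; only separate reporting of Q4W time, if chosen, would add a derivation.

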1.3 STUDY RATIONALE AND BENEFIT-RISK ASSESSMENT

This study is designed to assess the long-term safety and tolerability of IT administered RO7234292 in patients who have completed or have participated in other F. Hoffmann-La Roche, Ltd.–sponsored (hereafter referred to as Roche) and/or Genentech-sponsored studies in HD in the development program for RO7234292. Presently, there are no therapies available to stop or slow the clinical progression of HD, which is relentless until patients experience premature death. The ASO RO7234292 is designed to target the cause of HD and offers the potential to meet this unmet medical need.

To date, nonclinical and clinical data support further investigation of RO7234292 in patients with HD. Current planned or ongoing studies in the RO7234292 clinical development plan are designed for durations of up to approximately 2 years. This study is designed to collect safety data in a larger number of patients and will also study the

benefit and potential risks of RO7234292 when administered by IT bolus injection Q8W or every 16 weeks (Q16W) over a longer period.

Review of preliminary 9-month safety and tolerability data for RO7234292 from the Phase II OLE (Study BN40697) suggested that, relative to the Q4W treatment regimen, the Q8W treatment regimen may be more suitable for chronic IT dosing, as evidenced by improved adherence to the less frequent regimen. This is supported by observations of fewer overall AEs, decreased proportion of patients with moderate AEs, and fewer AEs considered possibly related to study drug in the Q8W regimen compared to the Q4W regimen (for details see the RO7234292 Investigator's Brochure).

There were no acute safety concerns meriting a change to the ongoing Phase II OLE study protocol (Study BN40697). However, given the 9-month CSF mHTT results, which suggested a longer than anticipated duration of effect of RO7234292 on CSF mHTT lowering, it is not necessary to use a Q4W paradigm to test the dose rationale. As a result, the results from OLE Study BN40697 justified a change in Study BN40955 to explore less frequent dosing regimens by continuing the Q8W RO7234292 arm and replacing the Q4W arm with a Q16W arm.

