2.1 SAFETY OBJECTIVE

The safety objective for this study is to evaluate the safety and tolerability of RO7234292 on the basis of the following endpoints:

- Incidence and severity of AEs, with severity determined according to the Adverse Event Severity Grading Scale (see [Table 3](#))
- Change from baseline in targeted vital signs
- Change from baseline in physical findings
- Change from baseline in neurological findings
- Change from baseline in behavioral findings, as assessed by the Columbia-Suicide Severity Rating Scale (C-SSRS)
- Change from baseline in cognition
- Change from baseline in targeted ECG results
- Change from baseline in targeted clinical laboratory test results
- Relationship between laboratory parameter change and safety-targeted endpoints
- Relationship between magnetic resonance imaging (MRI) parameter change and safety-targeted endpoints

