3.2 END OF STUDY AND LENGTH OF STUDY

The end of this study is defined as the date when the last patient, last visit occurs. The end of the study is expected to occur a minimum of 6 months after the last patient is enrolled.

The total length of the study, from enrollment of the first patient to the end of the study, is expected to be approximately 6 years. It is expected that patients may *participate for* a minimum of 6 months and a maximum of approximately 6 years in Study BN40955.

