5.1.1 Known Risks Associated with Lumbar Puncture

Post-lumbar puncture syndrome, spinal hematoma, and meningitis (see Sections 5.1.1.1–5.1.1.3) are potential risks associated with LP.

In the completed Phase I/IIa study, the most commonly reported AEs across all treatment groups (RO7234292, N=34; placebo, N=12) were procedural pain (54% of patients) and post-LP syndrome (37% of patients).

In the recently completed Phase II OLE Study BN40697, potential LP procedure-associated selected AEs were reported with similar incidence across the cohorts despite the difference in dosing frequency (16 patients [69.6%] in the Q4W cohort and 17 patients [73.9%] in the Q8W cohort). Overall, the most frequently reported event was procedural pain (41.3%). In the ongoing Phase III Study BN40423, patients enrolled under Protocol Versions 1–3 (receiving Q4W blinded treatment) were discontinued following discontinuation of the Q4W dosing. These patients' treatment assignments are now unblinded and hereby referred to as original design cohort (ODC). In the ODC, potential LP procedure associated selected AEs were reported with similar incidence across the three cohorts (17 patients [47.2%] in the placebo cohort, 14 patients [40%] in the Q4W cohorts, and 17 patients [47.2%] in the Q8W cohort). Overall, the events reported with highest incidence were procedural pain and post-lumbar puncture syndrome (14% each).

As of 07 August 2020, in the ongoing Study BN40955, potential LP procedure associated selected AEs were reported in 30 patients [22.9%] in the Q8W cohort and 11 patients [15.1%] in the Q16W cohort. Overall the most frequently reported event was procedural pain (9.2% in the Q8W cohort and 4.1% in the Q16W cohort). Many of the complications associated with LP can be avoided by the mandatory use of a 24G atraumatic needle with a stylet, adherence to procedural guidelines (see LP manual and instructional video), and careful assessment of the patient, including neurologic examination with fundoscopy both prior to and post-LP procedure. Lumbar puncture should be avoided when a contraindication is present.

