5.1.3 Management of Patients who Experience Adverse Events

5.1.3.1 Dose Modifications

No dose modifications are permitted in this study, whether by varying the amount of study drug volume injected or the frequency of procedure per protocol (i.e., all participants will receive 20 mL of study drug at every study drug administration either on a Q8W or Q16W basis as assigned by IxRS).

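### Section 6.5 reports AE incidence with no exposure, person-time, fixed-time or per-procedure measure, so pooled percentages mix risk with follow-up and number of lumbar punctures

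*Combined protocol and SAP*

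**What the plan says.** Protocol Section 6.5 plans: "The incidence of AEs will be summarized on the basis of body systems and dictionary preferred terms". It adds: "The incidence of AEs by severity and relationship to study drug or study procedure and incidence of marked abnormal laboratory test results will be provided". All safety data, AEs included, are to be listed and "summarized by treatment for each assessment time using descriptive statistics". The matching endpoint in Section 2.1 is "Incidence and severity of AEs, with severity determined according to the Adverse Event Severity Grading Scale".

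Incidence is not defined. Nothing in Section 6 names person-years, time to first event, risk at a stated time, events per LP, or exposure by arm. Sections 6.6 and 6.9 leave further modelling to the SAP; Section 6.5 does not.

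Other sections bear on time at risk and number of procedures:

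- Section 3.2 expects patients to take part for "a minimum of 6 months and a maximum of approximately 6 years in Study BN40955".
- Section 5.3.1 ends AE reporting 5 months after the final dose. Sections 3.1.1 and 4.5 pause dosing from 22 March 2021 and continue safety follow-up to study completion.
- Section 5.1.3.1 has drug given "either on a Q8W or Q16W basis as assigned by IxRS". Appendix 2b puts LPs at every 16 weeks in both arms during the pause.
- Section 1.3 describes "continuing the Q8W RO7234292 arm and replacing the Q4W arm with a Q16W arm".
- Section 5.1.1 reports LP-associated AEs in this study up to 7 August 2020: "30 patients [22.9%] in the Q8W cohort and 11 patients [15.1%] in the Q16W cohort".

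**The concern.** A percentage of patients with at least one event is a risk only when the period it covers is stated and is roughly the same for everyone. Here patients enter over time from five preceding studies (Appendix 11), and dosing stopped for all of them on one calendar date. Someone dosed once just before the pause and someone dosed since the study opened would count equally in the denominator.

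LP-associated events raise a further question. While dosing continues, Q8W patients have nearly twice as many LPs as Q16W patients. A per-patient table cannot show whether a higher Q8W percentage comes from more procedures, longer observation or a higher risk per procedure.

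At stake is whether the main safety table can say how often events occur, when they arise, and how the two regimens compare.

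**Working it through.** **1. What kind of figure the protocol reports.** The denominators behind Section 5.1.1 are not printed, but they can be recovered. 30/131 = 22.9% and 11/73 = 15.1%, and no other whole-number denominators round to those values. The same denominators reproduce the post-LP syndrome figures in Section 5.1.1.1: 7/131 = 5.3% and 2/73 = 2.7%. These are crude per-patient proportions. That supports reading incidence in Section 6.5 the same way, although the section does not say so.

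**2. Effect of follow-up alone.** At a constant event rate r, the crude percentage after time t is 1 − exp(−r·t). The rate r = 0.2 per year is an illustration, not a protocol figure.

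- Short window: one dose plus 5 months, t = 5/12. 1 − exp(−0.083) = 8.0%.
- Long window: the documents give no first-dose date. I assume it falls between January 2018 and January 2020, with no dose after 22 March 2021. Adding 5 months gives 22 August 2021, so the maximum is about 1.6 to 3.6 years. 1 − exp(−0.32) = 27%; 1 − exp(−0.72) = 51%.

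The same underlying rate therefore gives anything from 8% to 27–51%.

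**3. Number of LPs.** From the visit weeks in Appendix 2a, dosing through Week 97 means 13 LPs on Q8W (Weeks 1, 9, …, 97) and 7 on Q16W (Weeks 1, 17, …, 97). With an assumed risk q = 2% per LP in both arms and independent LPs, 1 − (1 − q)^k gives 23.1% for k = 13 and 13.2% for k = 7. The arms differ although the risk per LP is equal.

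**4. What 22.9% versus 15.1% can support.** The crude ratio is 1.52. On the cumulative-hazard scale, −ln(1 − 30/131) = 0.260 and −ln(1 − 11/73) = 0.163, a ratio of 1.59. Dividing by an assumed follow-up ratio (Q8W to Q16W), and then by 2 for dosing frequency, gives:

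| Assumed follow-up ratio | Rate ratio per unit time | Rate ratio per LP |
|---|---|---|
| 0.5 | 3.18 | 1.59 |
| 1.0 | 1.59 | 0.80 |
| 1.5 | 1.06 | 0.53 |
| 2.0 | 0.80 | 0.40 |

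The direction of the comparison depends on a quantity that neither the protocol nor the planned tables provide.

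**The case against.** Several points on the other side stand.

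- Section 6.5 plans more than one pooled percentage. It includes individual listings, AEs by relationship to drug or procedure, and summaries by assessment time. The last is a partial safeguard only, because no AE intervals or at-risk denominators are defined. The exposure-response work in Section 6.7 concerns drug exposure derived from PK modelling, not time at risk.
- More LPs are part of the Q8W regimen. Over equal, stated time, the per-patient percentage is a valid regimen-level risk, and per-LP risk is an additional question.
- The study is descriptive with no hypothesis test, so interpretation is affected, not error rates.
- A single rate per patient-year assumes a roughly constant hazard, which is doubtful for procedure-linked events and across a dosing pause. Such rates should not displace the crude table.

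A reader might also infer three stronger things that the documents do not support.

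- *Twelve-fold variation in time at risk* (6 months to 6 years; 9.5% versus 69.9% at 0.2 per year). Section 3.2 describes time in study, whereas Section 5.3.1 closes AE reporting 5 months after the final dose.
- *Longer follow-up on Q8W as a fact.* It is likely, since Q16W was added by amendment while Q8W continued. However, Section 3.1.1 randomly allocates patients already on Q4W in this study to either regimen, so early entrants are in both arms. No follow-up by arm is given.
- *Equal risk per LP as the explanation of 22.9% versus 15.1%.* With 48 weeks in each arm (7 and 4 LPs), 1 − (0.771)^(1/7) = 3.6% per LP, which predicts 13.8% on Q16W, close to the observed 15.1%. With 72 weeks on Q8W and 48 on Q16W (10 and 4 LPs), 1 − (0.771)^(1/10) = 2.6%, which predicts 9.9%. Equal per-LP risk is one scenario, under equal follow-up. Chance is not excluded either: the difference is 7.8 points, with a 95% CI of about −3 to +19 using the recovered denominators.

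**Conclusion.** The gap is real and worth correcting. Section 6 specifies no measure that relates AEs to time or procedures, while time under AE observation varies widely between patients and probably between arms. The illustrated spread, about 8% against 27–51% at one constant rate, rests on the assumed rate of 0.2 per year and the assumed first-dose dates. The LP counts of 13 and 7 through Week 97 come directly from the visit schedule. Actual exposure-adjusted rates cannot be computed from the documents, which give neither person-years nor LP counts by arm.

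The time at risk is itself undefined. Section 5.3.1 stops AE reporting 5 months after the final dose, Sections 3.1.1 and 4.5 continue safety follow-up to completion, and the protocol does not say what counts as the final dose for a patient whose dosing is paused. These passages must be reconciled before any denominator can be fixed.

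**What to change.** Keep the crude incidence table and add to Section 6.5:

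1. Exposure by arm: person-years under AE observation, doses and LPs.
2. First AEs and first SAEs per 100 patient-years at risk with 95% CI, split into on-dosing and paused time.
3. Kaplan-Meier cumulative incidence at 6, 12 and 24 months, with numbers at risk, for AEs of interest.
4. LP-associated AEs per 100 LPs, beside the per-patient figure.

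Reconcile Section 5.3.1 with Sections 3.1.1 and 4.5, and state when a patient's at-risk time starts and ends during the pause.

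The cost is SAP wording and a few extra tables from visit, dose and AE dates already collected, with no added patient burden. These tables will not make the arms comparable by themselves. Assignment is partly non-random (Table 1), and exposure adjustment does not remove that confounding.
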